-  FU amyloid PET scans at Weeks 78 and 104 will only be conducted at selected sites for participants enrolled in the longitudinal amyloid PET substudy and may be scheduled within a window of -21 to +7 days. Amyloid PET must be conducted using only the Sponsor-approved radiotracer and the same radiotracer used for baseline amyloid PET scan. A QC-passing Screening amyloid PET scan is required to continue in the longitudinal amyloid PET substudy. For participants consenting to both amyloid and tau PET substudies, the amyloid and tau PET scans should be performed on separate days (cannot be performed on the same day). For participants consenting to both CSF and PET substudies, if collected on the same day as a PET scan, CSF should be collected prior to PET. For participants in the amyloid PET longitudinal substudy who withdraw before Week 78, PET assessment will be collected at ET Visit only if withdrawal occurs > 6 months after the previous amyloid PET scan. For all women of childbearing potential, a pregnancy test must be performed within 24 hours prior to every PET scan.
-  FU tau PET scans at Weeks 78 and 104 should be collected in a subset of participants in the longitudinal tau PET substudy at selected sites and may be scheduled within a window of -21 to +7 days. Tau PET must be conducted using only the Sponsor-approved radiotracer and the same tracer used for baseline tau PET scan. A QC-passing screening tau PET scan is required to continue in the longitudinal tau PET substudy. For participants consenting to both amyloid and tau PET substudies, the amyloid and tau PET scans must be performed on different days (cannot be performed on the same day). For participants consenting to both CSF and PET substudies, if collected on the same day as a PET scan, CSF should be collected prior to PET. For participants in the tau PET longitudinal substudy who withdraw before Week 78, PET assessment will be collected at ET Visit only if withdrawal occurs > 6 months after the previous amyloid PET scan. For all women of childbearing potential, a pregnancy test must be performed within 24 hours prior to every PET scan.

 Two versions of the QoL-AD questionnaire will be completed: the participant's self-reported version and the informant-reported version describing the participant.

17 AEs and SAEs related to the PET radiotracer will also be monitored and reported.

Table 3: Abbreviated Schedule of Activities for Participants Who Discontinue Study Treatment but Remain in the Study

Study Week 	12	24	40	50/52	64	78	88	104	106	_	UV for
Study Day	85 ± 3	169 ± 3	281 ± 3	351 ± 3	449± 3	547 ± 3	617 ± 3	729/743 ± 3	743 ± 3	ET 	ARIA 
Physical Examination		X	X	X	X		X	X		X	
Neurological Examination		X	X	X	X		X	X		X	
12-Lead ECG				X				X		X	
Vital Signs	X	X	X	X	X		X	X		X	X
Hematology, Blood Chemistry, and Urinalysis				X				X		X	
Urine Pregnancy Test 	X	X	X	X	X		X	X			
Coagulation Panel 				X		X		X		X	
CSF Collection 				X		X		X		X	
Amyloid PET 						X					
Tau PET 						X					
Brain MRI								X		X	X
		Clin	ical Scales,	Patient-Repo	orted Outcon	ies, QoL, and	HEOR Mea	sures			
Diagnostic Verification Form				X		X			X	X	
MMSE				X		X			X	X	
CDR				X		X			X	X	
ADAS-Cog13				X		X			X	X	
ADCS-ADL-MCI				X		X			X	X	
NPI-10				X		X			X	X	
C-SSRS-SLV	X	X	X	X	X	X	X	X	X	X	X

Study Week 	12	24	40	50/52	64	78	88	104	106	БТ 2	UV for	
Study Day	85 ± 3	169 ± 3	281 ± 3	351 ± 3	449± 3	547 ± 3	617 ± 3	729/743 ± 3	743 ± 3	ET 	ARIA 	
RUD-Lite				X		X			X	X		
QoL-AD 				X		X			X	X		
				Routi	ne Safety Mo	nitoring						
Concomitant Therapy and Procedures		Monitor and record continuously throughout the study										
AE Reporting		Monitor and record continuously throughout the study 										
SAE Reporting	Monitor and record continuously throughout the study 											

<sup>1 Participants who discontinue study treatment and withdraw from the study prematurely will attend an ET visit, and additionally a FU Visit, 18 weeks after their final dose, as noted in Table 2. Participants who discontinue treatment but agree to stay in the study will follow the abbreviated visit schedule outlined here. Participants will begin this Schedule of Activities at the visit that most closely follows study treatment discontinuation.

<sup>2 Participants who withdraw voluntarily from the study prematurely are to return to the site for an ET Visit, unless withdrawal is due to death or withdrawal of consent. If the participant discontinues treatment within 3 months of the previous efficacy assessment visit, and no significant changes in cognitive status are suspected by the Investigator, clinical efficacy assessments are not required. In such cases, the site should notify the Sponsor and the Medical Monitor.

<sup>3 For the frequency of required brain MRI assessments sample collection for participants who develop ARIA-E and/or ARIA-H, see Section 5.3.1. This includes PK sample collection at the first unscheduled visit for ARIA monitoring per episode only. For the frequency of brain MRI assessments following resolution of ARIA and resumption of dosing, see Section 5.3.1.6. For management of recurrent ARIA, see Section 5.3.1.7.

<sup>4 A urine pregnancy test is required for women of childbearing potential only if the last dose of study treatment was less than 24 weeks before the clinic visit.

<sup>6 Coagulation panels, including PT, PTT, INR, and platelet count, must be performed within 35 days before the LP. If a participant, in the opinion of the Investigator, is at increased bleeding risk, the coagulation panel should be repeated within 7 days before the LP, if necessary. These repeat tests may be performed locally to facilitate a timely review of the results. Before any LP can be performed, the results of the most recent coagulation panel, concomitant medications, and overall general bleeding risk must be reviewed by the Investigator and must indicate that the LP can be performed safely. When the coagulation panel is performed at a visit that includes hematology testing, the platelet count should be done only once.

<sup>7 Before any LP can be performed, the results of the most recent coagulation panel, concomitant medications, and overall general bleeding risk must be reviewed by the Investigator and must indicate that the LP can be performed safely. An LP should not be performed if the Investigator suspects the presence of intracranial hypertension clinically or radiologically.

<sup>8 FU amyloid PET scan at Weeks 78 will only be conducted at selected sites for participants enrolled in the longitudinal amyloid PET substudy and may be scheduled within a window of -21 to +7 days. Amyloid PET must be conducted using only the Sponsor-approved radiotracer and the same radiotracer used for

baseline amyloid PET scan. A QC-passing screening amyloid PET scan is required to continue in the longitudinal amyloid PET substudy. For participants consenting to both amyloid and tau PET substudies, the amyloid and tau PET scans must be performed on different days (cannot be performed on the same day). For participants consenting to both CSF and PET substudies, if collected on the same day as a PET scan, CSF should be collected prior to PET. For participants in the amyloid PET longitudinal substudy who withdraw before Week 78, PET assessment will be collected at ET Visit only if withdrawal occurs > 6 months after the previous amyloid PET scan. For all women of childbearing potential, a pregnancy test must be performed within 24 hours prior to every PET scan.

9 FU tau PET scan at Weeks 78will only be collected in a subset of participants enrolled in the longitudinal tau PET substudy at selected sites and may be scheduled within a window of -21 to +7 days. Tau PET must be conducted using only the Sponsor-approved radiotracer. A QC-passing Screening tau PET scan is required to continue in the longitudinal tau PET substudy. For participants consenting to both amyloid and tau PET substudies, the amyloid and tau PET scans must be performed on different days (cannot be performed on the same day). For participants consenting to both CSF and PET substudies, if collected on the same day as a PET scan, CSF should be collected prior to PET. For participants in the tau PET longitudinal substudy who withdraw before Week 78, PET assessment will be collected at ET Visit only if withdrawal occurs > 6 months after the previous amyloid PET scan. For all women of childbearing potential, a pregnancy test must be performed within 24 hours prior to every PET scan.

<sup>12Two versions of the QoL-AD questionnaire will be completed: the participant's self-reported version and the informant-reported version describing the participant.

<sup>13AEs and SAEs related to the PET radiotracer will also be monitored and reported.

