# 4. STUDY OBJECTIVES AND ENDPOINTS

Primary Objective	Primary Endpoints
To verify the clinical benefit of monthly doses of aducanumab in slowing cognitive and functional impairment as measured by changes in the CDR-SB score as compared with placebo in participants with early Alzheimer's disease.	Change from baseline in CDR-SB score at Week 78
Key Secondary Objectives	Key Secondary Endpoints
To assess the effect of monthly doses of aducanumab as compared with placebo on clinical decline as measured by the iADRS	Change from baseline in iADRS score at Week 78
To assess the effect of monthly doses of aducanumab as compared with placebo on clinical decline as measured by ADCS-ADL-MCI	Change from baseline in ADCS-ADL-MCI score at Week 78
To assess the effect of monthly doses of aducanumab as compared with placebo on clinical decline as measured by ADAS-Cog13	Change from baseline in ADAS-Cog13 score at Week 78
To assess the effect of monthly doses of aducanumab as compared with placebo on clinical decline as measured by the MMSE	Change from baseline in MMSE score at Week 78
To assess the effect of monthly doses of aducanumab as compared with placebo on clinical decline as measured by NPI-10	Change from baseline in NPI-10 score at Week 78
Secondary Objectives	Secondary Endpoints
To assess the effect of aducanumab on cerebral amyloid plaque level as measured by amyloid PET imaging (where available, in a subset of sites and participants)	Change from baseline in amyloid PET signal at Week 78 and Week 104
To assess the effect of aducanumab on cerebral tau levels as measured by tau PET	Change from baseline in tau PET signal at Week 78 and Week 104

imaging (where available, in a subset of sites and participants)		
To assess the effect of monthly doses of aducanumab as compared with placebo on clinical decline as measured by the CDR-SB score	Change from baseline in CDR-SB score at Week 106	
To assess the effect of monthly doses of aducanumab as compared with placebo on clinical decline as measured by iADRS	Change from baseline in iADRS score at Week 106	
To assess the effect of monthly doses of aducanumab as compared with placebo on clinical decline as measured by ADCS-ADL-MCI	Change from baseline in ADCS-ADL-MCI score at Week 106	
To assess the effect of monthly doses of aducanumab as compared with placebo on clinical decline as measured by ADAS-Cog13	Change from baseline in ADAS-Cog13 score at Week 106	

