# 9.4. **Pharmacodynamic Assessments** Serial measurements of disease- or treatment-related will be assessed in all participants. The pharmacodynamic properties of aducanumab will be confirmed through analyses of blood samples that will include, but are not limited to,

# **Optional Substudies**

The following substudies will be conducted in a subset of sites and participants, where available. Investigator participation in these substudies is optional and contingent upon approval by the ethics committee or IRB. If the Investigator is not participating in a substudy, or if the tests described below are not approved by the Investigator's ethics committee and/or IRB, the relevant section of the ICF will not be applicable to that site. Informed consents must be recorded in the CRF. Approximately 400 participants are expected to enroll in each of the 3 Participating in multiple substudies (where available) is highly encouraged. Historical CSF samples or PET scans are not acceptable for participants in the longitudinal

[figure not shown]
The pharmacodynamic properties of aducanumab will be confirmed through the following longitudinal substudies:

1. Measurement of amyloid plaque burden in certain areas of the brain as measured by amyloid PET

Participants who consent to this optional longitudinal PET substudy will undergo 3 PET scans (Screening, Week 78, and Week 104). Only sites with capabilities to perform amyloid PET with Sponsor-approved tracer will be allowed to perform this assessment. Detailed PET scanning protocols will be described in a separate procedural manual for PET.

2. Measurement of neurofibrillary tangle burden in certain areas of the brain as measured by tau PET

Participants who consent to this optional longitudinal PET substudy will undergo 3 PET scans (Screening, Week 78, and Week 104). Only sites with capabilities to perform tau PET with Sponsor-approved tracer will be allowed to perform this assessment. Detailed PET scanning protocols will be described in a separate procedural manual for PET.

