#### 12.2.2.4. Considerations for Efficacy Endpoint Analysis

In analyses performed on the FAS, participants will be analyzed based on the intent-to-treat principle according to their randomized treatment assignment regardless of treatment received. The primary estimand on the treatment effect of aducanumab is for the primary endpoint based on the continuous variable of change from baseline scores in CDR-SB. This analysis is conducted for an estimand with a treatment policy strategy to handle all ICEs, with the following attributes as outlined by ICH E9 (R1):

- Analysis set: all participants in the FAS
- Variable: the change from baseline scores in CDR-SB at Week 78 regardless of ICEs
- Analysis set level summary: LS mean difference from MMRM model in change from baseline between aducanumab dose and placebo
- ICEs and strategies for addressing ICEs: all observed data to be included regardless of ICEs

The ICEs include treatment discontinuation or a change in concomitant use of Alzheimer's disease symptomatic medication.

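### Participants who permanently stop treatment but stay in the study have no Week 104 amyloid or tau PET in Table 3, although Section 9.4 gives every substudy participant that scan; the tau early-termination rule is timed from the wrong scan

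*Protocol*

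**What the plan says.** Table 3 in Protocol Section 1.3 applies to one group: "Participants who discontinue treatment but agree to stay in the study will follow the abbreviated visit schedule outlined here". Its amyloid and tau PET rows carry a single mark, at Week 78. Footnote 8 says "FU amyloid PET scan at Weeks 78 will only be conducted at selected sites for participants enrolled in the longitudinal amyloid PET substudy", and footnote 9 says "FU tau PET scan at Weeks 78will only be collected in a subset of participants enrolled in the longitudinal tau PET substudy". Table 2, the main schedule, marks both scans at Weeks 78 and 104. Its footnote 13 begins "FU amyloid PET scans at Weeks 78 and 104 will only be conducted at selected sites", and footnote 14 gives the same two weeks for tau.

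Section 9.4 uses the same sentence for each PET substudy: "Participants who consent to this optional longitudinal PET substudy will undergo 3 PET scans (Screening, Week 78, and Week 104". It makes no exception for people off treatment. The amyloid endpoint in Section 4 is "Change from baseline in amyloid PET signal at Week 78 and Week 104", with a matching tau endpoint. Both are secondary endpoints, analysed by MMRM (Section 12.2.2.7). For efficacy analyses on the FAS, Section 12.2.2.4 says "participants will be analyzed based on the intent-to-treat principle according to their randomized treatment assignment regardless of treatment received".

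For substudy participants who withdraw from the study before Week 78, the footnotes add an early-termination (ET) rule: "PET assessment will be collected at ET Visit only if withdrawal occurs > 6 months after the previous amyloid PET scan". The tau footnotes (Table 2 footnote 14, Table 3 footnote 9) use these same words, so they refer to the amyloid scan. The ET column of Table 3 is blank in both PET rows. The ET column of Table 2 is marked in both.

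**The concern.** Two parts of the protocol disagree on whether a substudy participant who has permanently stopped dosing is scanned at Week 104. A lighter visit schedule does not by itself explain the gap. Table 3 keeps a Week 104 visit with CSF collection and brain MRI, and keeps the clinical scales at Week 106. The two PET measures are the only Section 4 secondary endpoints that lose their last timepoint for these participants.

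If Table 3 were followed, Week 104 PET values would be absent by schedule for everyone who had permanently stopped. An FAS analysis by randomised arm would then take their Week 104 values from a model fitted to those who had not stopped. If amyloid or tau change differs after stopping, the Week 104 estimate drifts towards an effect in people who keep dosing. Certain ARIA findings require permanent discontinuation (Section 8.1), so the gap could plausibly be larger on aducanumab.

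The tau ET rule is a separate slip. It decides whether to repeat a tau scan by the age of a different scan.

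**Working it through.** The plan gives no power or precision figure for the PET endpoints, so there is none to reproduce.

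**1. Scans scheduled per substudy participant**

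| Source | Screening | Week 78 | Week 104 | Total |
|---|---|---|---|---|
| Table 2, footnotes 13 and 14 | yes (from Table 1) | yes | yes | 3 |
| Table 3, footnotes 8 and 9 | yes (from Table 1) | yes | no | 2 |
| Section 9.4 | yes | yes | yes | 3 |

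The ET scan does not close the gap. It is limited to withdrawal before Week 78, so it is not a Week 104 scan. Participants whose dosing is only suspended have not discontinued. They stay on Table 2 and keep the Week 104 scan.

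**2. Number affected.** Section 9.4 expects about 400 per substudy. At 2:1 that is 400 × 2/3 ≈ 267 on aducanumab and 133 on placebo. The documents give no rate of stopping treatment while staying in the study. Assume p = 10% to 25% on aducanumab: 267 × 0.10 ≈ 27 and 267 × 0.25 ≈ 67 participants with no Week 104 scan by schedule.

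**3. Complete-case illustration.** Set the effect in continuing participants to 1. Assume those who stopped keep a fraction r, and that stopping placebo changes nothing. The all-randomised mean is 1 − p(1 − r), so the overstatement is 1/(1 − p(1 − r)) − 1.

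- r = 0.5: p = 0.10 gives 1/0.95 − 1 = 5.3%; p = 0.25 gives 1/0.875 − 1 = 14.3%.
- r = 1: no overstatement.
- r = 0: p = 0.10 gives 1/0.90 − 1 = 11.1%; p = 0.25 gives 1/0.75 − 1 = 33.3%.

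**4. What the MMRM would recover.** Take people who stop before Week 78, with r = 0.5 at both visits and a regression slope b of Week 104 on Week 78. Their modelled Week 104 value is 1 − 0.5b, against a true 0.5. The overstatement is 0.5p(1 − b)/(1 − 0.5p).

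- p = 0.10: b = 0.9 gives 0.005/0.95 = 0.5%; b = 0.7 gives 0.015/0.95 = 1.6%.
- p = 0.25: b = 0.9 gives 0.0125/0.875 = 1.4%; b = 0.7 gives 0.0375/0.875 = 4.3%.

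The slope range is an assumption. For those who stop between Weeks 78 and 104, the Week 78 scan is an on-treatment value and does not provide this correction.

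**5. Tau ET rule.** Table 1 footnote 22 lets a participant reach the tau scan on a positive amyloid PET or CSF result, so a CSF-qualified participant may have no previous amyloid scan. Inclusion criterion 5 accepts a historical amyloid scan up to 18 months old. If that scan is already more than 6 months old, the condition is met however recent the baseline tau scan is.

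**6. Calendar.** SAP Section 9.1 dates the first dose 27 July 2022. Week 104 (Day 729) for that participant is 24 July 2024, or 3 July 2024 with the 21-day early window. Dosing was offered only until 1 May 2024 (SAP Section 2.2.3), which is that participant's Day 645. SAP Section 2.2.5 stopped the PET substudies, and Section 6.1 does not analyse secondary endpoints.

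**The case against.** The strongest reply is that the shorter PET schedule may be intended. Section 9 opens by sending the reader to Section 1.3 for timing, and Sections 8.1 and 8.3 say discontinuers attend only a subset of visits. Section 5.1 describes what the substudies involve and does not promise each person every scan. This stands as a possible explanation, but it leaves the Section 9.4 sentence wrong as written. The plural week label in footnotes 8 and 9 equally suggests that a second week was dropped in drafting.

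The treatment-policy estimand is stated explicitly only for CDR-SB. The intent-to-treat sentence says which arm a participant is analysed in, not which scans are taken. That also stands: the conflict for PET is with the general FAS analysis, not with a declared PET estimand.

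A reader might infer from ARIA-E of 35.2% versus 2.7% that missing Week 104 scans would be heavily imbalanced. The documents do not support this. Those figures are incidence. Under Section 5.3.1.1, nonserious ARIA-E leads to continued dosing or to suspension with possible resumption. Some imbalance remains plausible, but its size is unknown. A reader might also take 5% to 14% as the bias of the planned analysis. It is not, because it ignores the Week 78 scan, and nothing in the documents supports applying the halved effect to tau.

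On the blank ET cells, footnotes 8 and 9 state the scan in words, Table 2 marks it, and Table 3 footnote 1 refers withdrawing participants to Table 2. That is a formatting mismatch; the rule does not fail.

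**Conclusion.** The conflict holds on the text: two scheduled scans under Table 3 against three in Section 9.4, for endpoints defined at Weeks 78 and 104. As designed, Week 104 PET would be scheduled only for participants who had not permanently discontinued, and the MMRM would model the rest from them. The distortion cannot be sized from the documents. Under the assumed 10% to 25% stopping and half-retained effect, it is 5% to 14% by complete case and roughly 0.5% to 4% by MMRM for those who stop before Week 78. The complete-case figure is the upper illustration for those inputs, and would be larger if less of the effect were retained. The direction of any bias is clearer for amyloid than for tau.

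The tau ET rule names the wrong scan, whatever is decided about Week 104.

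The scope is limited to two secondary endpoints in optional substudies, outside the testing hierarchy of Section 12.2.2.3. A reader might infer that reported PET results are compromised. They are not: no participant could have reached Week 104, the substudies were stopped, and no secondary endpoint is analysed. This is a flaw in the protocol design, worth correcting in any reuse of it.

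**What to change.** Reconcile Table 3 with Section 9.4 in one of two ways:

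- add Week 104 to both PET rows of Table 3 and to footnotes 8 and 9; or
- correct the three-scan sentence in Section 9.4 for both substudies, and state in Sections 4 and 12.2.2.7 that Week 104 PET is estimated from participants who have not permanently discontinued.

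In Table 2 footnote 14 and Table 3 footnote 9, replace the reference to the previous amyloid scan with the previous tau scan. Mark PET in Table 3's ET column so that it agrees with its own footnotes and with Table 2.

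The first option costs table marks, footnote text and the extra scans, which Section 9.4 already describes and which fall at a visit Table 3 already contains. The second costs wording only. Neither changes the trial's sample size or power. With the study terminated, the correction matters for any later protocol that reuses these tables.
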